13.0 CRITERIA FOR REMOVAL FROM STUDY

If at any time the patient desires to quit participation in the study or is found to be ineligible for the protocol as designated in the section on Criteria for Subject Eligibility the patient will be removed from the study.

14.0 BIOSTATISTICS

The purpose of this pilot study is to assess the feasibility of utilizing multi-beam IMRT in the adjuvant treatment of the breast and regional lymph nodes of women with node-positive breast cancer requiring coverage of the internal mammary lymph nodes. Infeasibility is defined in Section 12.1 in detail. A feasibility rate of at least 90% is required, ie, treatment can be successfully planned and delivered for at least 90% of the patients.

For this study, we require 100 evaluable patients for analysis of the primary endpoint. We define a patient who is evaluable for analysis as one who has completed their 5-7 month follow-up and 5-7 month PFT. A patient is inevaluable for analysis if he or she is not able to complete the 5-7 month follow-up and 5-7 month PFT. According to our experience, since there may be patients enrolled on study who are later found to be inevaluable, our maximum target accrual is 120 patients. However, if we are able to accrue 100 evaluable patients before we reach the maximum target accrual, we will close the study to accrual.

The multi-beam IMRT method is considered feasible if the treatment plan can be attempted for at least 90 patients among the 100 patients to be treated and evaluated. With this rule, the probability of considering the multi-beam IMRT feasible is 99%, 58%, 10% and 0.6% if the true feasibility rate is 0.95, 0.90, 0.85 and 0.80, respectively. An exact 95% confidence interval for the feasibility rate will also be

computed using the binomial distribution. With the sample size of 100 patients, and assuming for example the observed feasibility rate is 90%, the resulting confidence interval will be (84%, 95%).

For the secondary objectives, we will use descriptive summary for most endpoints and apply appropriate tests when necessary. Specifically, the demographic and clinical characteristics of the sample will be summarized by descriptive statistics. The number and reasons of infeasible patients will be tabulated.

- 1) The incidences of acute and late cutaneous toxicity and its 95% confidence intervals will be calculated.
- 2) The incidences of acute and late subcutaneous fibrosis and its 95% confidence intervals will be calculated.
- 3) The incidences of acute and late RP and its 95% confidence intervals will be calculated.
- 4) The local-regional recurrence rate associated with using multi-beam IMRT will be estimated using the Kaplan-Meier product limit method. If competing risks are present in the data (eg, patients may die without any recurrence), we will modify the analysis plan to accommodate the competing risks.
- 5) To evaluate patient set-up reproducibility in breast cancer patients treated with multi-beam IMRT using daily 3D position verification, the difference in initial set up and final set up will be recorded in mm on a daily basis. Basic descriptive statistics will be tabulated at the CoT.

Because the Grade 4 toxicity rate is expected to be very low, safety is not a major issue for this study. Therefore a stopping rule is not needed here.

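### The exact 95% confidence interval printed for 90 of 100 feasible patients (84% to 95%) is wrong; the exact binomial interval is 82.4% to 95.1%

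*Combined protocol and SAP*

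**What the plan says.** All the relevant text is in Section 14.0 (Biostatistics) of the combined protocol and SAP.

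- **Sample size:** "we require 100 evaluable patients for analysis of the primary endpoint".
- **Decision rule:** "considered feasible if the treatment plan can be attempted for at least 90 patients among the 100 patients to be treated and evaluated".
- **Operating characteristics of that rule:** passing probabilities of 99%, 58%, 10% and 0.6% for true rates of 0.95, 0.90, 0.85 and 0.80.
- **Interval method:** the promise opens with "An exact 95% confidence interval for the feasibility rate will also be", and the distribution named for it is the binomial.
- **Worked example, for 100 patients:** "assuming for example the observed feasibility rate is 90%, the resulting confidence interval will be (84%, 95", so the limits given are 84% and 95%.

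No other interval method is named for the primary endpoint, and no other numerical interval is given for it.

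**The concern.** The plan fixes everything needed to check the example: the confidence level, the method, the number of patients and the observed rate. The answer should therefore be reproducible without any assumption, and it is not. The lower limit is visibly too close to 90% for an exact interval with 100 patients.

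The lower limit is the one that matters here. The example is set at 90 of 100, the smallest count that passes. A reader who wants to know how poor the true feasibility rate could be after a bare pass is told that rates below 84% are excluded. The promised method excludes only rates below 82.4%. It is also the only statement of how precisely 100 patients will estimate the primary endpoint. If whatever calculation produced the pair were used again at the analysis, the reported interval would be wrong as well.

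**Working it through.** **Inputs (all from Section 14.0).** n = 100; observed rate 90%, so x = 90; 95% confidence, taken as two-sided because two limits are given; exact binomial method.

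**Step 1. Confirm n and the model from the plan's own figures.** P(X ≥ 90) for X ~ Binomial(100, p):

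| True rate p | Computed | Stated |
|---|---|---|
| 0.95 | 0.9885 | 99% |
| 0.90 | 0.5832 | 58% |
| 0.85 | 0.0994 | 10% |
| 0.80 | 0.0057 | 0.6% |

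All four agree, so n = 100 and the binomial model are what the authors used for the decision rule.

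**Step 2. Exact interval at x = 90, n = 100.**

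- Lower limit: the 0.025 quantile of Beta(x, n − x + 1) = Beta(90, 11), which is 0.8238.
- Upper limit: the 0.975 quantile of Beta(x + 1, n − x) = Beta(91, 10), which is 0.9510.

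The interval is 82.4% to 95.1%. The stated upper limit is right to rounding and the stated lower limit is not.

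**Step 3. Direct check of the lower limit.** The exact lower limit is the true rate at which P(X ≥ 90) equals 0.025. At p = 0.84 this probability is 0.061, more than twice 0.025, so 84% is not the limit. At p = 0.8238 it is 0.025.

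**Step 4. Could another method give the printed pair?** Intervals for 90 of 100, in per cent:

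| Method | 95% | 90% |
|---|---|---|
| Exact (Clopper-Pearson) | 82.4 to 95.1 | 83.6 to 94.5 |
| Wald | 84.1 to 95.9 | 85.1 to 94.9 |
| Wald, continuity-corrected | 83.6 to 96.4 | not run |
| Wilson | 82.6 to 94.5 | 84.0 to 93.9 |
| Wilson, continuity-corrected | 82.0 to 94.8 | not run |
| Agresti-Coull | 82.4 to 94.7 | 83.9 to 94.0 |
| Jeffreys | 83.0 to 94.7 | 84.2 to 94.1 |
| Mid-P | 82.9 to 94.8 | 84.2 to 94.2 |
| Inversion of the binomial test | 82.6 to 94.7 | 83.5 to 94.0 |
| Logit | 82.4 to 94.5 | not run |

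None rounds to (84, 95). At 95%, Wald comes nearest, but it rounds to (84, 96) and is not exact.

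**Step 5. Probable source.** The 2.5% and 97.5% quantiles of Binomial(100, 0.90) are 84 and 95. The printed pair is therefore consistent with the central 95% range of the observed count when the true rate is 0.90. That is not a confidence interval for the true rate after observing 90 of 100. This explanation is an inference; the documents do not show how the pair was obtained.

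**Step 6. Size of the error.** Lower limit: 84 − 82.4 = 1.6 points too high. Width: 95.10 − 82.38 = 12.72 points, against 95 − 84 = 11 stated. The stated interval is 1.72 / 12.72 = 13.5% too narrow. For scale, an exact lower limit of 84% at an observed 90% needs about 150 patients (135 of 150 gives 84.0% to 94.3%).

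**The case against.** The best defence is that this is a wrong number in an illustration. Feasibility is declared on a count, and the interval plays no part in that decision. The plan introduces the interval as an addition, after operating characteristics that are correct and that already show how the rule behaves when the true rate is low: about a 10% chance of passing at 0.85 and 0.6% at 0.80. The upper limit is right, and only one limit is off, by less than two points. The text prescribes an exact binomial interval for the analysis, so an analyst who follows it will get the right answer. Nothing in the documents shows that the quantile calculation would be used again.

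Most of this stands as a statement about impact. The justification of 100 patients does not collapse, the decision rule is untouched, and the risk to the final analysis is only conditional. None of it makes the printed figure correct. Section 14.0 names a method and states a result that the method does not produce, and nothing elsewhere in the documents corrects it. Exact, applied to a binomial proportion, is normally read as Clopper-Pearson, so naming the method is a clarification; changing the number is the necessary correction.

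**Conclusion.** The concern holds. For 90 of 100 the exact 95% interval is 82.4% to 95.1%, not 84% to 95%. The planned precision is overstated by 1.6 points at the lower limit and by 1.7 points in width. The conclusion rests only on inputs stated in Section 14.0 and on reading the interval as two-sided; the 90% versions and the other methods do not rescue the printed pair. The practical effect is modest: the pass rule, the operating characteristics and the sample size are unchanged. It should still be corrected, because it is a false figure for the primary endpoint, placed at the pass boundary, and it errs in the favourable direction.

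**What to change.** In Section 14.0, replace the printed interval with (82%, 95%), or 82.4% to 95.1% if one decimal is preferred. State that the interval is two-sided Clopper-Pearson, both in the planning example and for the final analysis. The same paragraph could name the method for the 95% intervals promised for cutaneous toxicity, fibrosis and radiation pneumonitis, for which none is given.

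The cost is an edit of a sentence or two. The stated precision becomes slightly less favourable; sample size, decision rule and study conduct do not change.

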2.2 Secondary Objectives

The endpoints in these objectives are descriptive and will form the basis for designing future studies. In keeping with the feasibility nature of this study, endpoints will be observed at least through 5-7 months following the completion of radiation therapy. The Common Terminology Criteria for Adverse Events (CTCAE version 3.0) will be used for grading toxicities (see [Appendix 1](#); the complete toxicity grading system is available for review at <http://ctep.cancer.gov>).

- To evaluate the rate and severity of both acute and late cutaneous toxicity
- To evaluate the rate and severity of late subcutaneous fibrosis
- To evaluate the rate and severity of radiation pneumonitis (RP)
- To evaluate local-regional control rates
- To evaluate patient set-up reproducibility in breast cancer patients treated with multi-beam IMRT

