3.2 Toxicities of Comprehensive Radiation Therapy

3.2.1 Acute Toxicities

The toxicity of comprehensive radiation therapy has been well described (15). Acute toxicity is defined as those effects that occur during a course of radiation therapy or within 90 days of its completion. Essentially all patients experience skin erythema, which may progress to desquamation in a fraction of patients. A mild pharyngitis is rarely seen. Fatigue can develop in up to 40% of patients. Acute side effects generally resolve within several weeks of the completion of radiation therapy and only rarely cause a treatment interruption. Acute toxicities to the skin and pharynx are typically graded using the CTCAE version 3. Relevant sections of the CTCAE are included in Appendix 1.

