Secondly, the proportion of patients who received immediate reconstruction after mastectomy with an ipsilateral implant has increased considerably over the past 4 years. The presence of an implant or temporary expander often poses technical challenges in delivering a homogenous dose to the chest wall secondary to the sharp slope of the implant on the chest wall, compared to a flat chest wall. In addition, the number of patients who underwent contralateral prophylactic mastectomy (CPM) simultaneously in addition to ipsilateral mastectomy has also dramatically increased in our department over the past year. Reconstruction with bilateral permanent implants frequently follows bilateral mastectomies and is the most common form of immediate reconstruction offered to bilateral mastectomy patients at MSKCC. We have simulated 60 patients with bilateral implants since 2008 to the present time (11/09), compared to 49 patients in a three-year time period between 2004 and 2007.

This increase in the number of bilateral implant reconstructions parallels both national trends in increased use of CPM over the past decade(43), as well as trends here at MSKCC. A retrospective study of CPM utilization at MSKCC demonstrated that the rate of CPM paralleled the use of MRI and increased from 7% to 25% between 1997 and 2005 (abstract presented by King et al at SABCS 2009). The presence of an implant/temporary expander can be problematic when planning radiation treatments to the chest wall and regional lymph nodes. Optimizing beam angles such that the target structures are covered, while avoiding the contralateral implant, lung, and heart is technically challenging. These patients could therefore potentially benefit from multi-beam IMRT.

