6.0 CRITERIA FOR SUBJECT ELIGIBILITY

6.1 Subject Inclusion Criteria

1. Female gender
2. Age \geq 18 years
3. An invasive primary breast cancer of any histology arising from breast parenchyma
4. Patient must be status post mastectomy or partial mastectomy with an assessment of axillary nodes via sentinel lymph node biopsy and/or axillary lymph node dissection
5. Pathologic confirmation of metastatic disease in at least one regional lymph node. Regional lymph nodes are defined as the ipsilateral axillary lymph nodes, ipsilateral supraclavicular lymph nodes, and ipsilateral internal mammary lymph nodes. Thus, any T stage is allowed as long as the N stage is \geq 1 and M stage is 0.
6. Patient signed study-specific consent form.

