10.0 EVALUATION DURING TREATMENT/INTERVENTION

Tests and Observation	Pre-Treatment	During IMRT	Completion of IMRT (CoT) ⁴	6-12 weeks after CoT	5-7 mo after CoT	Follow up ¹
History	X ²			X	X	X
Physical	X ²	X ⁵	X	X	X	X
(Feasible Plan Generated/Delivered)	X					
Daily Setup Data			X			
PFTs	X				X	
BMI	X					
Mammogram ³	X					X
Clinical Assessment of Acute Skin Toxicity		X ⁵	X	X		
Late Subcutaneous Fibrosis					X	X
Late Cutaneous Toxicity					X	X

Clinical Assessment of RP				X	X	X
RP CAP Questionnaire	X			X	X	X
BreastQ Questionnaire (for mastectomy patients)	X				X	
Pregnancy test (if relevant)	X					
¹ Patients will be seen at 12-14 months following the CoT and then every 6-8 months for up to 5 years of follow up. ² Done within 120 days of RT start ³ Mammogram at baseline and then annually or more often if clinically indicated (only applicable for lumpectomy patients). The annual mammogram will be based on the patient's last follow up mammogram (+/- 1 month window). For patients found to have distant metastasis after treatment, annual mammograms will no longer be required. ⁴ Done ±10 days of the last radiation treatment (CoT) ⁵ Done at least two times during radiation treatment including the CoT timepoint						

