11.0 TOXICITIES/SIDE EFFECTS

Patients will be assessed for toxicities related to radiation treatment. Potential acute side effects include skin reactions, erythema, edema, hyperpigmentation, desquamation, fatigue, and/or RP. The incidences of these side effects with conventional radiation techniques to the breast and lymph nodes are described in Section 3.2.1.

Lactating and pregnant women are also excluded because of potential teratogenic effects of radiotherapy that may be harmful to the developing fetus or nursing infant.

Patients will be assessed for late toxicities (>3 months post radiation) as described in Section 3.2.2, including skin toxicity and/or RP. Toxicities will be scored according to the CTCAE, version 3.0 criteria.

No side effects are expected to result from the daily imaging used for target localization.

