12.2 Assessment of Secondary Objectives

Various metrics will be gathered at the following times: Pre-treatment (defined as within 45 days prior to the start of radiation treatment, excluding the History and Physical and mammogram), completion of therapy (done \pm 10 days of the last radiation treatment), 6-12 weeks following CoT, 5-7 months following CoT, and 12-14 months following CoT. These metrics are described below.

a. To evaluate the rate and severity of both acute and late cutaneous toxicity

The radiation oncologist will score cutaneous toxicity at the end of treatment (\pm 10 days of the last radiation treatment) and at 6-12 weeks following CoT. Late cutaneous toxicity will be scored at 5-7 months and 12-14 months following CoT, utilizing the CTCAE version 3.0 grading system. Some of these toxicities are not appropriately measured by the CTCAE and a more suitable scale is attached in Appendix 2.

b. To evaluate the rate and severity of late subcutaneous fibrosis

The radiation oncologist will score late subcutaneous fibrosis at 5-7 months and 12-14 months following CoT, utilizing the CTCAE version 3.0 grading system. Some of these toxicities are not appropriately measured by the CTCAE and a more suitable scale is attached in Appendix 2.

c. To evaluate the rate and severity of RP.

RP rates will be assessed by CTCAE version 3.0 grading system at 6-12 weeks, 5-7 months and at 12-14 months following CoT. We will also administer the CAP questionnaire pretreatment, at 6-12 weeks, 5-7 months and at 12-14 months following CoT. PFTs will be obtained at pretreatment and 5-7 months following CoT.

d. To evaluate local-regional control rates

Locoregional recurrence is defined as tumor in the ipsilateral breast/chest wall and/or ipsilateral regional lymph nodes (axillary, supraclavicular or internal mammary). Time to local recurrence will be calculated from the date of the completion of radiation treatment to the date of the biopsy proving recurrence or the first CT, PET, or MRI scan demonstrating recurrence. Kaplan-Meier methods will be used to assess local-regional control.

e. To evaluate patient set-up reproducibility in breast cancer patients treated with multi-beam IMRT using daily 3D position verification.

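### Section 14 plans an acute fibrosis incidence that no visit is scheduled to measure, and the late fibrosis and late skin rates have no pre-treatment grade to separate new change from surgical change.

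*Combined protocol and SAP*

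**What the plan says.** Section 14.0, item 2, plans this analysis: "The incidences of acute and late subcutaneous fibrosis and its 95% confidence intervals will be calculated".

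The rest of the protocol is narrower. Section 2.2 sets the objective as "To evaluate the rate and severity of late subcutaneous fibrosis". The Section 10.0 table has one fibrosis row, "Late Subcutaneous Fibrosis", marked at 5-7 months and at later follow-up. Section 12.2(b) agrees: "The radiation oncologist will score late subcutaneous fibrosis at 5-7 months and 12-14 months following CoT". Section 3.2.1 fixes the acute period: "Acute toxicity is defined as those effects that occur during a course of radiation therapy or within 90 days of its completion". Section 11.0 places late toxicity beyond 3 months.

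On baseline status, Section 6.1 requires surgery for every patient: "Patient must be status post mastectomy or partial mastectomy with an assessment of axillary nodes". Section 3.3 adds that "the proportion of patients who received immediate reconstruction after mastectomy with an ipsilateral implant has increased considerably over the past 4 years". Section 8.0 and the Pre-Treatment column of the Section 10.0 table include lung baselines (CAP questionnaire, PFTs) and BreastQ for mastectomy patients, but no skin or fibrosis grade. A history and physical is required, ungraded, and may be up to 120 days old when radiation starts. Section 12.2(a) scores late cutaneous toxicity at 5-7 and 12-14 months, and no rule in Sections 12.2 or 14.0 relates these grades to the patient's condition before radiation.

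**The concern.** There are two separate problems.

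The first is non-measurement. An incidence with a confidence interval is promised for acute fibrosis, but no visit in the acute period is scheduled to grade it.

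The second is the meaning of the late rates. Incidence implies new events. Scar induration and skin change after mastectomy, partial mastectomy, axillary surgery or implant reconstruction may already be present when radiation starts. With no baseline grade, a late grade of 1 or more shows that change is present, not that it is new. The study has one arm, so no comparator shows the surgical background. Section 2.2 intends these rates to inform the design of future studies, and a late rate inflated by surgical change would be carried into them.

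**Working it through.** **Plan's own figures.** Section 14.0 gives no figure for skin toxicity or fibrosis. Its design figures concern the primary rule (at least 90 of 100 feasible). Exact binomial tails at true rates 0.95, 0.90, 0.85 and 0.80 are 98.85%, 58.32%, 9.94% and 0.57%, against the stated 99%, 58%, 10% and 0.6%. They reproduce, and nothing below enters them.

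**Acute fibrosis: visits against the acute period.**
- Acute period (Section 3.2.1): during radiation to day 90 after completion.
- Visits in that period (Section 10.0): during IMRT, at completion (CoT), and 6-12 weeks after, which is 6 × 7 = 42 to 12 × 7 = 84 days. The toxicity row marked at all three is acute skin toxicity; fibrosis is marked at none.
- First fibrosis grade: 5 × 30.44 ≈ 152 to 7 × 30.44 ≈ 213 days.

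Scheduled fibrosis assessments in the acute period: 0. If the empty cell were nevertheless tabulated as 0 of 100, the exact 95% upper limit would be 1 − 0.025^(1/100) = 3.6%. That would look precise but would reflect only the absence of scheduled assessment.

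**Late rates without a baseline.** Let b be the proportion with change of grade 1 or more before radiation and r the proportion who truly develop new change. Neither is in the documents; both are assumptions. If the two are independent, and pre-existing change persists and is graded as toxicity at the late visit:

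observed rate = b + (1 − b) × r

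| b (assumed) | r = 10% | r = 20% |
|---|---|---|
| 0% | 10.0% | 20% |
| 5% | 14.5% | 24% |
| 10% | 19.0% | 28% |
| 20% | 28.0% | 36% |

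For example, b = 20% and r = 20% gives 0.20 + 0.80 × 0.20 = 0.36.

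Exact 95% intervals with 100 evaluable patients:
- r = 10%, b = 10%: 19 of 100, 11.8% to 28.1%, which excludes the true 10%.
- r = 20%, b = 10%: 28 of 100, 19.5% to 37.9%, which still covers 20%.
- r = 20%, b = 20%: 36 of 100, 26.6% to 46.2%, which excludes 20%.

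Whether the bias exceeds sampling error therefore depends on b and r.

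**Acute skin toxicity.** Section 3.2.1 says that nearly every patient develops erythema. With r near 100%, b + (1 − b) × 1 = 1 whatever b is. The any-grade acute skin rate is hardly touched.

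**The case against.** The strongest reply is that the first problem is one stray word and the second is partly covered. Items 1 to 3 of Section 14.0 share the same acute-and-late wording, and three other places agree on late fibrosis only, so a carried-over phrase is the simplest explanation. Section 10.1 also has maximum CTCAE toxicities submitted at completion without limiting them to skin, so a fibrosis grade might be recorded incidentally. This stands as an explanation, but an incidental record is not a scheduled assessment of every patient and cannot support an incidence.

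On the baseline, the radiation oncologist scores the toxicity, Section 11.0 says that the interest is in effects related to radiation, and a pre-treatment physical exists. Late effects are graded repeatedly, from 5-7 months through follow-up of up to 5 years, so onset and course can help to distinguish new change from stable scarring. This stands too. A reader might infer that neither rate can be attributed to radiation at all, or that late effects are graded only once; the documents support neither. What remains is that the examination is ungraded, may be 120 days old, and is not used by any stated rule. Relationship to treatment is listed for SAE reports and in the grade 4 or higher criterion of Section 12.1, not for routine skin or fibrosis grades. The contents of Appendices 1 and 2 and the case report forms were not available, so a provision there cannot be excluded.

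Finally, the endpoints are descriptive and no decision rests on routine skin or fibrosis grades. That limits the weight of the point. It does not justify calling a prevalence an incidence.

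**Conclusion.** The point holds in two limited parts. The acute fibrosis incidence in Section 14.0, item 2, contradicts Sections 2.2, 10.0 and 12.2(b) and cannot be estimated from the scheduled visits. This is a failure to measure, not a question of attribution, and nothing in the documents says that the rate would be reported as zero.

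The late fibrosis and late cutaneous rates, as planned, are post-treatment prevalences that can include pre-existing surgical change. Attribution is weakened, not impossible. The size is unknown: an observed rate of 20-36% when 20% is truly new and 0-20% is pre-existing illustrates the mechanism under assumed independence and persistence, and does not show that bias of this size exists here. A reader might extend the concern to acute skin toxicity; for any-grade rates the protocol's own description of erythema argues against that. The primary endpoint and the sample size are unaffected. The change is inexpensive and worth making, but it is not a condition for the study's main conclusion.

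**What to change.** - **Section 14.0, item 2:** delete 'acute and'. If an acute fibrosis rate is really wanted, fibrosis would instead have to be graded at completion and at the 6-12 week visit.
- **Section 10.0 table (and the Section 8.0 list):** add a Pre-Treatment grade for cutaneous change and for subcutaneous fibrosis, on the same CTCAE version 3.0 and Appendix 2 scales, at the existing pre-treatment physical or at simulation, after definitive surgery.
- **Sections 12.2(a), 12.2(b) and 14.0, items 1 and 2:** report the late incidence as a grade new or worsened relative to the patient's own pre-treatment grade, and show the raw grade beside it.
- **Patients already treated:** no baseline grade can be recovered, so report their raw grades and label the rate as post-treatment prevalence.

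The cost is two form lines at a contact that already takes place, plus the wording changes. The limit is that a baseline grade separates new from pre-existing change; in a single-arm study it does not prove that radiation was the cause.
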